7 TREATMENT OF SUBJECTS

Study drug is to be administered only to subjects who have provided informed consent and meet all of the criteria outlined in [Sections 6.1](#), Subject Inclusion Criteria, and [6.2](#), Subject Exclusion Criteria.

7.1 Procedures/Parameters to be Measured

See the Study Flowchart ([Table 1](#), beginning on page 12) for the timing of the procedures to be performed at each visit.

All subjects will be assessed by scheduled clinical, laboratory, and other diagnostic assessments throughout the study. Subjects will be treated on an outpatient basis, unless hospitalization is required for other reasons.

Subjects must voluntarily sign and date the study-specific Institutional Review Board (IRB)/Ethics Committee (EC)-approved informed consent before any study-related procedures (with the exception of disease assessment for screening if it was completed as part of standard of care) are performed.

All screening assessments are to be performed within **21 days** prior to first study drug dose, unless otherwise specified.

The day of first study drug administration will be considered **Day 1** of the study.

Clinic visits will take place according to the schedule of assessments. The visit window of ± 2 working days does not apply to study drug administration. Visit assessments will be performed prior to administration of the study drug for that day.

If significant changes from baseline are noted during the course of the study, additional unscheduled clinic visits may be undertaken by the investigator, or requested by the sponsor, in order to determine both the relevance of the finding(s) and the duration of the event(s).

All end-of-treatment assessments are to be performed within **7 days** following the last study drug dose unless delayed due to the occurrence of an adverse event. Note: subjects starting any new anti-cancer therapy must complete the End-of-Treatment Visit prior to starting the new anti-cancer therapy.

A follow-up visit will be performed **30 days (± 7 days)** following the last dose of study drug.

After the 30-Day Follow-up visit, subjects will be contacted once every 3 months by the site to collect long-term survival data.

Informed Consent

All subjects must take part in the informed consent process. Adequate time must be allowed for the subject to ask questions and make a voluntary decision. No protocol specific procedures, including screening procedures are to be performed until the subject has signed and dated an IRB/EC approved informed consent form (ICF). The signing of the ICF can occur outside of the 21-day screening period; however, all protocol related procedures must only be performed after signing of the consent.

Demographic/Medical History

A complete medical history will be taken. Information to be documented includes demographic information (age, gender, ethnicity, and race), prior and ongoing medical illnesses and conditions, and surgical procedures (not related to the primary diagnosis).

Note: Data will be collected according to local regulations.

Disease History

This information should include the date of initial diagnosis, date of most recent relapse, staging at study entry, prior anti-cancer therapies (including radiation therapy) and/or surgeries, current signs and symptoms of malignant disease, metastatic sites of disease, and measurement of target lesions. For prior antineoplastic treatments, start and end dates of treatments, and method by which disease progression was confirmed (eg, CT, MRI).

IMDC Risk Category

The IMDC risk category will be determined according to the IMDC criteria (see [Appendix H](#)).

Prior and Concomitant Medications

Prior medications will be collected at the time of screening. All concomitant medications will be collected from time the subject signs the ICF throughout the subject's participation in the study, including a period of 30 days after their last dose of study drug.

Adverse Event Assessments

Refer to Section 12 for information regarding adverse events reporting requirements.

Eastern Cooperative Oncology Group (ECOG) Performance Status

Subject's performance status will be assessed using the ECOG performance status tool (see [Appendix B](#)).

Vital Sign Measurements

Vital sign measurements will be collected after the subject has been sitting for 5 minutes. Vital sign assessments will include measurements of diastolic and systolic blood pressure (mmHg), heart rate (beats per minute), respiration rate (breaths per minute), and body temperature (Celsius).

Physical Examination

A complete physical examination (PE) will be performed at screening by a physician or staff member who is qualified to perform such examinations (eg, physician's assistant, or nurse

practitioner). The complete PE will include a thorough review of all body systems and include measurements of weight (kg) and height (cm).

At all other visits throughout the study, a directed PE, including weight (kg), will be completed in a targeted manner covering body systems related to the subject's disease or relevant findings in the complete PE performed at the Screening visit.

Hematology

Hematology assessments are to include complete blood count (CBC) with differential and platelet count. Hematology evaluations should be increased in frequency in the event of a clinically significant hematologic toxicity.

Serum Chemistries

Serum chemistry assessments are to include measurements of sodium, potassium, chloride, bicarbonate (optional), blood urea nitrogen (BUN), creatinine, glucose, total bilirubin, direct bilirubin, AST, ALT, lactate dehydrogenase (LDH), alkaline phosphatase, calcium, magnesium, phosphorus, albumin, amylase, lipase, and total protein.

Thyroid Function Tests

Thyroid function tests are to include measurements of thyroid stimulating hormone (TSH), total T3 (triiodothyronine) (optional), and free T4 (thyroxine).

Coagulation Parameters

Coagulation parameter assessments are to include measurements of prothrombin time (PT) and/or international normalized ratio (INR), and partial thromboplastin time (PTT).

Urinalysis

Urinalysis assessments are to include determinations of protein, glucose, ketones, urobilinogen, occult blood, and microscopic sediment evaluation. A 24-hour urine for protein will be performed whenever protein is 4+.

Pregnancy Test

A serum pregnancy test will be performed on all females of childbearing potential within 7 days prior to the first dose of study drug.

12-Lead Electrocardiogram (ECG)

ECGs will be performed after subjects have been supine for approximately 10 minutes. Assessment of normal, abnormal, not clinically significant, and abnormal, clinically significant (with reason noted) will be collected in the electronic case report form (eCRFs).

Disease/Response Assessment

Disease and response assessments will be determined using RECIST (Version 1.1, [Appendix A](#)).

Disease/response assessment is to include disease classification (including details of the primary diagnosis and histological/cytological type and stage of disease at Screening) and diagnostic imaging / measurement of lesions.

The same method of assessment and the same technique should be used throughout the study. CT and MRI will be considered the standard method for evaluating disease status. All subjects should have a CT scan or MRI of the head, chest, abdomen, and pelvis at baseline. During subsequent disease/response assessments, a CT scan or MRI of the head will only be required if the subject had brain metastasis at baseline or new symptoms suggestive of brain metastasis. The location of target and non-target lesions and dimensions of target lesions will be documented on the subject's eCRF, where such information is available.

Response assessment and updates will be performed and documented. Response assessment will continue until the time of disease progression or start of another anti-cancer therapy.

If disease progression is documented at any time, no further imaging or lesion measurements will be required. Diagnostic studies documenting disease response must be available for review by the sponsor, if requested.

In the event of an objective response, the duration of the response will be determined from the day the initial response is observed (using screening/baseline images for comparison) to the day that progression is observed. Duration of disease stabilization will also be assessed (see Appendix A). In the case of stable disease (SD), follow-up measurements must have met the SD criteria at least once after study entry at a minimal interval of 8 weeks.

Pharmacokinetics

Blood samples for the analysis of pharmacokinetic parameters of tivozanib or sorafenib will be collected from all subjects. Samples will be collected at Cycle 1, Day 1- 4 hours post-dose and at Cycle 1, Day 15- pre-dose (within 2 hours before dosing).

Study Drug Administration Diary

A Study Drug Administration Diary will be provided to the study subjects at the start of each cycle. Diary information will be recorded and/or collected from each subject during study visits.

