- m. For subjects with stable disease or objective response at the time of treatment discontinuation, who discontinue for reasons other than radiological evidence of progressive disease, tumor assessments will continue to be collected (every 2 months during the first year [beginning from the date of the last scan performed prior to treatment discontinuation], every 3 months during the second year, and every 6 months thereafter) until disease progression is confirmed by independent radiology review or start of another therapy. A ±3 day visit window applies to tumor assessments for subjects that have discontinued study drug.
- n. Two blood samples for pharmacokinetic (PK) analysis will be collected at the following time points from all subjects: Cycle 1, Day 1- 4 hours post-dose and Cycle 1, Day 15- pre-dose (within 2 hours before dosing).
- o. After the 30-Day Follow-up visit, subjects will be contacted once every 3 months by the site to collect long-term survival data. Additional contacts may be made to support key analyses, such as the analysis of overall survival at the time of the final PFS analysis, and the final analysis of overall survival. A ±7 day window applies for the scheduled long term follow-up contacts.
- p. A ±2 day window applies to all visit procedures except study drug administration.
- q. The duration of treatment for tivozanib is 21 of 28 days, and for sorafenib is 28 of 28 days.
- r. All subjects will have an EOT visit when they permanently discontinue any further study treatment. The EOT visit will occur up to 7 days after the last dose of study drug. Assessments performed within 3 days of the EOT visit need not be repeated and may be documented as the EOT assessment (except for the response assessment which does not need to be repeated if performed within 30 days and showed progressive disease). Subjects starting new anti-cancer therapy after the last dose of study drug must complete the End of Treatment Visit assessments in advance of starting the new anti-cancer therapy.
- s. If additional visits are needed, these assessments may be obtained/ performed/ measured as clinically indicated.

TABLE OF CONTENTS

PROCEDURES IN CASE OF EMERGENCY	2
PROTOCOL SIGNATURE PAGE	3
1 SYNOPSIS.....	4
2 LIST OF ABBREVIATIONS AND EXPANDED TERM	20
3 INTRODUCTION	23
3.1 Background.....	23
3.2 Pharmacology	23
3.3 Safety Pharmacology	24
3.4 Toxicology	24
3.5 Pharmacokinetics	26
3.6 Previous Human Experience.....	26

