7.2.4 Duration of Study Treatment

Subjects with documented stable disease or an objective response may continue to receive therapy at the same dose and schedule until disease progression or unacceptable toxicities occur, or if other withdrawal criteria are met, as outlined in [Section 11.1](#).

Discontinuation: Subjects experiencing unacceptable toxicities will be discontinued from further study treatment. Subjects with radiological evidence of progressive disease (per RECIST Version 1.1) per investigator/local radiology assessment should continue treatment until progressive disease is verified by an independent radiologist. Images should be submitted for independent review as soon as possible (see Imaging Manual for specific instructions). Verification of progressive disease is not required in the following circumstance:

- Significant clinical deterioration that is compatible with progressive disease.

Subjects who have documented disease progression (as verified by an independent radiologist) will be discontinued from the study treatment.

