9 ASSESSMENT OF ACTIVITY

9.1 Disease Classification and Response Assessments

Data on disease classification and the duration of disease stabilization or any objective response, as well as the time to disease progression, will be collected for all subjects. Subjects will undergo disease assessment at screening (within 30 days prior to first dose of study drug) and every 8 weeks following Cycle 1, Day 1 until radiological disease progression is documented and confirmed by independent radiology review. Response will be determined by RECIST (Version 1.1) criteria ([Appendix A](#)).

Disease parameters to be assessed:

- Disease classification
- Diagnostic imaging/measurement of target lesions
- Response assessment.

Disease Classification

Details of the primary diagnosis should be documented at the Screening Visit. The histological/cytological type and stage of disease should be noted on the eCRF.

Diagnostic Imaging/Measurement of Lesions

Subjects should be followed with the same imaging procedure throughout this study; if progressive disease (PD) is documented at any time per RECIST Version 1.1, no further imaging or lesion measurements will be required after PD is verified by an independent radiologist; diagnostic studies documenting response must be available for sponsor review.

Response Assessment

Response will be assessed as detailed in [Appendix A](#) using RECIST criteria Version 1.1. All subjects who receive a minimum of 2 cycles of study drug will be considered evaluable for response assessment. All subjects who develop early progressive disease (regardless of the

duration of the study treatment) prior to response evaluation will be considered to have progressed on study.

The duration of any objective response is to be measured from the date the initial response is observed to the date that disease progression is observed. In the case of SD, follow-up assessments must have met the SD criteria at least once after study entry, at a minimal interval of 8 weeks.

Response Assessment Update

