3.2 Efficacy and Safety Variables

3.2.1 Efficacy Variables

Tumor response will be assessed using RECIST v1.1 criteria. Subjects will undergo assessments at screening and every 8 weeks following Cycle 1, Day 1 until radiological disease progression is documented and confirmed by independent radiology review. Evaluable subjects are those who receive at least 2 cycles of study drug.

Best overall response (BOR) is determined once all assessments from randomization until disease progression or death are recorded. In general, it is the best response across all assessments; however, confirmation of complete response (CR), partial response (PR), and stable disease (SD) will also be used in BOR determination. To confirm CR or PR changes in tumor measurements must be confirmed by repeat assessments that should be no less than 4 weeks (28 days) after the criteria for response are first met. To confirm SD, it must have occurred at least 8 weeks from Cycle 1, Day 1; otherwise, BOR will depend on subsequent assessments.

All subjects will be followed until death from any cause (unless the subject is lost to follow-up, withdraws consent for the entire study, or the sponsor terminates the study early). After the 30-Day Follow-up visit, subjects will be contacted once every 3 months by the site to collect long-term survival data. For subjects with ongoing objective response or disease stabilization at the time of treatment discontinuation, or for subjects who discontinue for reasons other than radiological evidence of progressive disease, tumor assessments will continue to be collected every 2 months during the first year (beginning from the date of the last scan performed prior to treatment discontinuation), every 3 months during the second year, and every 6 months thereafter until disease progression is confirmed by independent radiology review or the start of another anti-tumor therapy that includes anti-cancer surgery/procedure, anti-cancer radiotherapy, and anti-cancer systemic therapy.

Primary Efficacy Endpoint

PFS is defined as the time from randomization date to the first date of radiological PD or death date (due to any reason), whichever event is earlier. PFS in months will be calculated as: (first event date – randomization date + 1) * (12/365.25). Censoring will occur as follows:

- If there are no tumor assessments after randomization, PFS will be censored on the date of randomization.

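### The protocol gives two answers on when imaging for IRR-assessed PFS may stop and who is scanned off drug, leaving a narrow route to possibly informative censoring

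*Protocol*

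**What the plan says.** **When imaging stops.** Protocol 7.1 (Disease/Response Assessment) says "If disease progression is documented at any time, no further imaging or lesion measurements will be required" and names no assessor. Section 9.1 states the same rule with a condition: "no further imaging or lesion measurements will be required after PD is verified by an independent radiologist". It also sets 8-weekly scans "until radiological disease progression is documented and confirmed by independent radiology review".

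**End-of-treatment scan.** Table 1 note l and section 7.1.7 waive this scan only if a scan in the preceding 30 days showed progression confirmed by independent review. Table 1 note r waives it if a scan within 30 days showed progression, without that condition.

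**Off-drug scans.** Table 1 note m begins "For subjects with stable disease or objective response at the time of treatment discontinuation, who discontinue for reasons other than radiological evidence of progressive disease", so both conditions must hold. Sections 7.1.10, 7.2.5 and 9.1 carry the same double condition. The synopsis (dose interruption), 10.4.2, 10.4.4 and the closing text of 11.1 require only that the stop was for a reason other than radiological or RECIST progression. SAP 3.2.1 joins the two conditions with 'or': "or for subjects who discontinue for reasons other than radiological evidence of progressive disease, tumor assessments will continue to be collected".

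**Local progression calls.** Under 7.2.4 a subject with locally assessed progression "should continue treatment until progressive disease is verified by an independent radiologist". Then: "Verification of progressive disease is not required in the following circumstance", namely "Significant clinical deterioration that is compatible with progressive disease".

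**Censoring.** SAP 3.2.1 censors PFS at the last tumor assessment if follow-up ceases before objective progression. Protocol 14.3.4 makes the IRR the primary data source.

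**The concern.** An IRR endpoint needs scans to continue until the IRR itself records progression. If scanning ends on a local call that the IRR does not share, the subject is censored at a point chosen because progression looked imminent. That censoring is potentially informative. The trial is open-label, so early local calls could differ by arm, and the hazard ratio would then be biased. If they do not differ, IRR events are still lost. Sites that read different sections would also handle the same subject differently, and nothing in the analysis would show it.

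**Working it through.** **1. The plan's own figure.** Inputs (Protocol 14.2): medians 4 and 6 months, two-sided 5%, 90% power, 1:1 allocation, 255 events. With exponential PFS the hazard ratio is 4/6 = 0.667. Schoenfeld events = 4 × (1.960 + 1.282)² / (ln 0.667)² = 255.65, so 256 against 255 stated. Power is 89.9% at 255 events and 88.4% at the 242 targeted for the data cut-off (Protocol 5.3).

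**2. The passages side by side.**

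| Topic | Independent confirmation, or wider scanning | No such condition, or narrower scanning |
|---|---|---|
| Stop imaging | 9.1 | 7.1 |
| Waive end-of-treatment scan | Note l, 7.1.7 | Note r |
| Who is scanned off drug | Synopsis, 10.4.2, 10.4.4, 11.1, SAP 3.2.1 | Note m, 7.1.10, 7.2.5, 9.1 |

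Most off-drug passages do not say whose reading defines stable disease or radiological progression. Section 7.2.5 is the exception: the progression that excludes a subject there is the independently confirmed kind.

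**3. Two subjects followed through the text.**

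*Local progression, clinically well.* Under 7.2.4 and item 4 of 11.1 the subject stays on drug until verification, and under 9.1 is scanned every 8 weeks meanwhile. Scanning stops early only if a site takes the 7.1 sentence alone.

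*Local radiological progression plus clinical deterioration.* Verification is waived and drug stops.
- End-of-treatment scan: required by note l and 7.1.7 if the IRR has not confirmed progression; waived by note r.
- Later scans: under note m and 7.1.10 the subject is locally neither stable nor responding, so on a local reading is outside the rule.
- The closing text of 11.1 and sections 10.4.2 and 10.4.4 exclude stops for RECIST or radiological progression without naming the reader. Item 6 of 11.1 covers clinical progression only when RECIST is not met.
- Even the SAP's 'or' can miss this subject on a local reading.

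If the IRR reads the last scan as non-progression and no scan follows, SAP 3.2.1 censors there.

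**4. Illustrative size.** The documents give no local-versus-IRR discordance rate, so every share below is assumed. Simulation: 400,000 subjects per arm, exponential PFS, 56-day scans, follow-up cut at 21 months (15 enrollment + 6 follow-up). In the stated share of subjects, scanning stops one scan before IRR progression; this applies only when IRR progression falls at the second scan or later. The Cox model uses Breslow ties.

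| Share sorafenib / tivozanib | HR, medians 4 and 6 | HR, no true effect | Subjects with observed IRR event (medians 4 and 6) |
|---|---|---|---|
| 0 / 0 | 0.70 | 1.00 | 94% |
| 3% / 5% | 0.69 | 0.99 | 91% |
| 5% / 3% | 0.71 | 1.01 | 91% |
| 5% / 5% | 0.70 | 1.00 | 90% |
| 5% / 10% | 0.68 | 0.97 | 88% |
| 10% / 5% | 0.72 | 1.03 to 1.04 over repeat runs | 88% |

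The baseline is 0.70, not 0.667, because 8-weekly scans group the event times. The change from 0.70 is what matters.

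**5. Equal loss.** If 5% of 255 IRR events were lost in both arms, 255 × 0.95 = 242 remain and power is 88.4%. At 10%, 255 × 0.90 = 230 remain and power is 86.7%. If the trial instead waits for its event target, the cost is time rather than power.

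**The case against.** The strongest reply is that the rest of the protocol corrects the loose sentences. Sections 7.2.4 and 9.1 and item 4 of 11.1 keep a subject with an unconfirmed local call on drug and scanned. Note l and 7.1.7 call for an end-of-treatment scan in exactly the disputed case. Item 6 of 11.1 classes significant clinical deterioration as clinical progression that does not meet RECIST, so the closing text of 11.1 arguably requires scans to continue. Appendix A 1.4 asks sites to try to document objective progression after a stop for symptomatic deterioration. Most of this stands. A reader might infer from 7.1 that any unshared local call ends scanning, or that no section asks for another scan in the deterioration case. The documents do not support either reading.

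The reply does not remove the contradiction. Notes l and r cannot both apply to the same visit. Item 6 does not clearly fit a subject whose local scan does meet RECIST.

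The second reply is that the route is narrow. It needs local radiological progression, deterioration, an IRR non-progression reading, no new therapy and no prior death. That also stands: new therapy censors anyway, and death is an event in the PFS definition. One qualification is that Sensitivity Analysis #2 implies deaths after two or more missed assessments are otherwise treated differently, and SAP 3.2.1 states no such rule.

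Third, the sensitivity analyses help. #1 counts investigator and clinical progression as events, #2 counts new therapy, and #3 adds treatment discontinuation. They can show whether the result depends on this censoring. None recovers a missing IRR scan, and #4 acts only when a later progression is recorded.

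**Conclusion.** The contradiction is real and bears on the primary endpoint, but its reach is limited: subjects stopped with local radiological progression plus clinical deterioration, and any subject at a site that applies 7.1 or note r literally. The actual size is unknown. Under assumed shares of 3 to 10%, unequal by arm, the hazard ratio moves by about 0.01 to 0.04 in either direction. Equal shares leave it almost unchanged and cost IRR events.

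Three stronger inferences are not supported. Larger distortions need far more subjects to lose scans than this route plausibly supplies. Bias needs discordance that differs by arm, which an open-label design permits but no document shows. The slowing of PFS events that led to the 242-event cut-off should not be attributed to this gap; SAP 4.10 explains it by the few remaining subjects, who may not progress for some time. Severity is moderate: worth correcting, but not a reason to doubt that the trial can answer its primary question.

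**What to change.** Use one imaging rule in both documents.

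- Protocol 7.1 and Table 1 note r: add the condition already in 9.1 and note l, so that imaging stops, or the end-of-treatment scan is waived, only after progression is confirmed by the IRR.
- Table 1 note m, Protocol 7.1.10, 7.2.5, 9.1, 10.4.2, 10.4.4, 11.1 and the synopsis, and SAP 3.2.1: all subjects who stop study drug without IRR-confirmed progression, including those with locally assessed progression or clinical deterioration, continue scheduled scans until IRR-confirmed progression, new anti-cancer therapy, death or withdrawal.
- State in that rule that the IRR reading decides.

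This changes imaging wording only, not when drug is stopped. The cost is a protocol and SAP text change plus a few additional scheduled scans. Some of these subjects will be too ill to be scanned and some will start new therapy, so the rule will not recover every missing assessment.
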